#### Randomisation to 18 month follow up;

**Primary Aim:** We aim to carry out a pragmatic trial that will inform policy makers, commissioners of services and professionals about the potential of MST in a UK context, investigating whether the provision of MST could reduce the incidence of out of home placements for young people at risk of being removed from their homes because of antisocial behaviour, severe mental health problems, educational problems or unmet need. The trial will take referrals of families with an adolescent with severe antisocial behaviour problems who is considered to be at risk of custodial or other forms of out of home care. The trial will answer the question of whether MST can contribute to significantly reducing the rate of out of home placement

**Secondary Aim:** We will investigate whether MST is associated with (a) decrease in antisocial behaviour, (b) increase in young person's well-being, (c) improved educational outcomes and (d) improved family functioning. Moreover, we aim to establish the cost of MST relative to management as usual, and the cost-effectiveness of providing this intensive form of intervention against the background of costs incurred in the 18 months period following randomisation.

The immediate objectives of the trial are: (1) to confirm recruitment of ten MST service providers and agree on an acceptable protocol for randomisation of cases (month 3); (2) to recruit and train outcome assessors (OAs) to a predetermined level of reliability (month 4); (3) to identify a representative clinical sample of 700 young people to be recruited from ten sites (month 21); (4) to randomise 350 cases to MST and 350 to MAU (month 21 – this figure allows for a significant number who may not consent to enter the trial); (5) to assess outcome of randomised cases at 6, 12, 18, 24,30 and 36 months post recruitment (month 39); (6) to estimate the total social, health, educational and criminal justice cost of interventions at 18 months post-randomisation (month 42); (7) to identify the key cost and outcome drivers and the value for money of the treatments at 18 months (month 44) and (8) to analyse data, write reports and prepare papers for publication in peer reviewed journals 4 years after the commencement of the trial (month 48).

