Our primary outcome is incidence of out of home care, but we recognize that out of home care cannot be considered a negative outcome in all cases. We have therefore identified key forensic, family function and individual well being indicators which will be assessed at 6, 12, 18, 24, 36and 48 months after randomisation. It is important to delimit as far as possible the key moderators of the effects of MST and we will explore the moderating effects of callous and unemotional traits and severity of anti-social behaviour. In order to understand the way this new intervention impacts on current services, from the viewpoint of both the users and providers, we will also undertake a qualitative, interview based investigation of the key stakeholders in the service systematically sampled from the 9 sites.

**Design:** This will be a randomised controlled trial. Allocation will be by minimisation, controlling for number of past convictions, gender and age at onset of criminal behaviour. Minimisation will be necessary to limit the impact of factors that could easily influence treatment response. Treatment centre will also be included in the minimization stratification to control for differences between centres. Recruitment and treatment will take 18 months. Treatments will be offered over a period of three to six months for individual families. The primary outcome will be out of home placements at 18 months. Key outcomes will include court or pre-court disposal rates as at 18 months following randomisation with further follow-ups included in the initial consent, as long-term prevention is a central goal of the intervention. Other secondary endpoint measures will be total service and criminal justice sector costs over 18 months post-randomisation, wellbeing, drug misuse, and family functioning.

**Setting:** Treatments will be offered by services collaborating in this MST trial at the 9 pilot sites. The study will be conducted in three research hubs or centres: London (UCL and IoP), Cambridge and Leeds. Cambridge and Leeds will be responsible for data collection from 5 pilot sites while London will collect from 4, selected on the basis of geographical convenience.

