
The ethical principles of which the MST Supervisor, MST Therapists and Outcomes Assessor must be aware when speaking to the young person and his or her carer about participation in the study are:

There is no negative consequence for those who decline to participate;

There is no negative consequence for those who do participate;

Potential participants are informed of all that is expected of them, including benefits and risks that may be associated with participation;

Consent to participate is freely and voluntarily given, with full appreciation of the above; Participants understand that they can withdraw their consent to continued participation at any point in the process;

All information gathered about them will remain confidential; and

Anonymity is assured in that individual participants will not be identified in any report or document produced.

Second, the MST Supervisor, MST Therapists and Outcomes Assessor understand that, for the MST clinical trial, the implications of these standards are that potential participants must understand:

What MST entails, including the amount of time spent in the home, the intensity and duration of intervention and what is expected of the participants;

That young people who decline to participate in the clinical trial will receive the same level of intervention they would normally expect from the YOS (i.e. they will not be penalised for declining consent);

That half those who sign the consent forms will receive whatever intervention would have been available to them if no MST study had been underway;

That the decision about who gets MST is made randomly so each person has an equal chance of being selected;

That the services offered to the control group are not a placebo or are not inferior but rather constitute the typical services available to young offenders as MAU;

That participation in the clinical trial entails filling out questionnaires to gather background information and after discharge from treatment or approximately five months if not allocated to MST;

That the young person's school will be approached for information;

That the parent or carer and the young person are free to drop out of the MST condition;

That all information participants provide will remain confidential except in three circumstances: 1) A person under 16 is at risk as defined in the Children Act 1989

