Planned Intervention: Multi-systemic therapy is an integrative, manualised, licensed programme with a substantial evidence base for engaging young people exhibiting anti-social behaviour and their families. Adolescents with severe conduct problems (violence, drug abuse, school expulsion) will be treated over a period of 3-6 months with a community-based multicomponent treatment programme focused on the family but also engaging schools, neighbourhoods and community resources and administered by specifically trained professionals with relatively low caseloads. Young people and families requiring this approach are assumed to be resistant to engagement by existing services even though intensive outreach services may be required, probably associated with complex family problems including substance misuse and mental health problems that are likely to affect parenting. Adolescents and their families will receive a minimum of 3 and a maximum of 6 months of input from the MST team. The frequency of contact with the MST workers will be monitored but not controlled. It is expected that, as with MAU, some families will require briefer periods of treatment or may prematurely terminate treatment unilaterally. MST is going to be delivered by a team of at least 3 specially trained clinicians under the supervision of an MST supervisor, with weekly one hour conference calls for consultation with an MST services staff member. In addition, it is expected that MST therapists will have the support of local consultation from mental health professionals with post-graduate qualifications in disciplines such as social work, psychology or counselling. In view of the breadth and complexity of this input, it will be essential to monitor consultation as well as contact time of the MST team in order to arrive at accurate assessments of health and social care costs. It is essential that MST therapists and MST supervisors should not be allowed to see participants in the MAU arm of the trial, although professional consultants to the MST team may well be engaged in provision of MAU.

*Management as usual* MAU will be the standard care offered to adolescents and their families who meet eligibility criteria for the trial. This treatment is likely to be diverse and may involve no therapeutic intervention or individual or family orientated work. It is likely to be delivered by a wide range of practitioners with quite different theoretical orientations. The average duration of

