#### **Measures:**

Follow-up assessments will be at 6, 12, 18, 24, 36 and 48 months post randomisation, with primary outcomes collected until 5 years post randomisation.

(a) Principles of measurement: The measures will be made across multiple domains (specific to criminal behaviour, family function, user satisfaction, comorbid problems and economic costs), using multiple methods (interviews, questionnaires, records), and multiple sources (adolescent, parent, teachers) to maximise the clinical validity of the outcome assessments and minimise bias arising from any single source of information. Where possible, measures will be made by individuals blind to treatment allocation. Many of the measures have been selected because they are part of an ambitious project under-way in the Parenting Academy (Scott, Dabbs et al.) with a range of samples, including with a large sample of looked after children, which will provide UK norms against which the current sample may be compared.

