# Figure 2: Anticipated screening and consenting procedure and attrition rates

# **START** Systemic Therapy for At Risk Teens: Roadmap

egin:	Trial Year 1	Mar	Trial Year 2	Mar	Trial Year 3	Mar	Trial Year 4	Tr
lar 2009 Rec	cruitment Target 200	Phased 2010	Recruitment Target 450	2011	Recruitment Target 50	2012		Compl
	Staggered	outcomes		1		12 Month	18 month	Mar 20
Consultation	recruitment	assessment		Recru	itment Treatment &	Outcomes	Outcomes	
and set-up	begins	l begins		col	nplete 6-month Outcomes	complete	Complete	
phase	Jun 2009	Dec 2009		Ma	2011 complete Nov 2011	May 2012	November 2012	
group • Dev	Month 3-6	report forms and ran Recruit and train RAs	ation forms • Pilot client rec domisation systems • Participation in MST train MG and DMEC • Database	ing and settir	ng up of MST supervisors' g			-
Ongoing ree	Month 4-27 cruitment - geograpi	hically staggered ea	rly start sites at each Centre	• Administra	tion of pre-treatment measu	res • Randomisation		
Treatment -	Month 4-33 – duration of 3-6 mo	onths for families ran	domised to MST					
	Month						athlesses to final states	- 11 12
Collect treat	tment characteristic	; Information - 3 mon	ths post randomisation • Co	liect Econom	ic Data - 3 months post rand	domisation and 3 mol	nthiy up to final data c	collection
		Month 10-33						
	d secondary outcom	ie assessment at 6 r	nonths post randomisation -	minimum of	2 weeks after family comple	te MST		
Primary and			Month 16-39					
Primary and			MONULI 10-39					
	d secondary outcom	ie assessment at 12	months post randomisation	l				
Primary and			months post randomisation Month 22-	45				
Primary and			months post randomisation Month 22- months post randomisation	45				
Primary and			months post randomisation Month 22-	45				

 
Primary and
 
Primary and
 
	d secondary outcom	ne assessment at 18	months post randomisation Month 22- months post randomisation	45 45				

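### The protocol gives contradictory timing for the first follow-up, and two of its statements depend on arm, which puts first-visit secondary outcomes at risk

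*Protocol*

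**What the plan says.** Several places in the protocol bear on when the first follow-up takes place.

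- **Overview (3.1):** "key forensic, family function and individual well being indicators which will be assessed at 6, 12, 18, 24, 36and 48 months after randomisation". No distinction is made by arm.
- **Measures (3.11):** "Follow-up assessments will be at 6, 12, 18, 24, 36 and 48 months post randomisation". Again this applies to everyone.
- **Objectives (Randomisation to 18 month follow up):** "to assess outcome of randomised cases at 6, 12, 18, 24,30 and 36 months post recruitment". The first visit is again at 6 months, although counted from recruitment.
- **Methods of recruitment and consent (3.6), list of what potential participants must understand:** "filling out questionnaires to gather background information and after discharge from treatment or approximately five months if not allocated to MST". The trigger is discharge in the MST arm and a calendar time of about five months otherwise.
- **Scheduling Roadmap (3.19):** the primary and secondary assessment is placed at 6 months after randomisation, in months 10–33, with a minimum of "2 weeks after family comple" (the line breaks in the extracted text; it refers to completing MST).

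On the length of MST, Planned intervention (3.9) says: "Adolescents and their families will receive a minimum of 3 and a maximum of 6 months of input from the MST team". It also expects that "some families will require briefer periods of treatment or may prematurely terminate treatment unilaterally".

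Data analysis (3.16) analyses secondary outcomes at each time point by linear or logistic regression and uses random effects models for trajectories over time.

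**The concern.** A randomised comparison at a nominal time point needs the same elapsed time since randomisation in both arms. Two of the protocol's statements tie the first visit to the end of MST, which has no counterpart in the MAU arm. If either were followed, visits labelled 6 months could fall at different elapsed times by arm. These young people enter the trial around a crisis, and their behaviour may change with time whatever the treatment. Elapsed time would then be mixed with the treatment effect in the first-visit analyses, and the trajectory models would carry this forward if they used nominal visit times.

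There is a lesser worry about blinding. The protocol collects MST contact data from the sites so that assessors do not learn allocation. A visit scheduled from an MST completion date works against that precaution if the assessor sees the date. The protocol does not say whether the assessor would.

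**Working it through.** No power or sample size figure depends on this point. The figures to check are the roadmap's windows and the timing that each statement implies.

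**Inputs**
- Recruitment months 4–27, treatment months 4–33, 6-month assessment months 10–33 (Roadmap).
- MST duration *d* = 3 to 6 months (Planned intervention), possibly shorter.
- MAU contact at 6 months (Overview, Measures, Roadmap) or about 5 months (consent list).
- Two weeks = 2 ÷ (52/12) = 0.46 month.
- Assumption: MST starts at randomisation. The protocol gives no start delay and no visit window.

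**Step 1. Reproduce the roadmap window.** 4 + 6 = 10 and 27 + 6 = 33. The assessment window is exactly the recruitment window plus 6 months, so the roadmap itself counts the visit from randomisation.

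**Step 2. Test the two-week condition against the 6-month visit.** A visit at month 6 meets the condition only if *d* + 0.46 ≤ 6, that is, *d* ≤ 5.54. A full course gives 6 + 0.46 = 6.46 months, so the condition and the time point cannot both hold.

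**Step 3. Test it against the window.** A family randomised at the end of recruitment with a full course finishes at 27 + 6 = 33. Its earliest permitted visit is 33 + 0.46 = 33.46, after the window closes.

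**Step 4. Offset for one family, MST minus MAU**

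| Statement followed | Formula | *d* = 3 | *d* = 5 | *d* = 6 |
|---|---|---|---|---|
| Overview, Measures | 6 − 6 | 0 | 0 | 0 |
| Roadmap | max(0, *d* + 0.46 − 6) | 0 | 0 | +0.46 |
| Consent list | *d* − 5 | −2 | 0 | +1 |

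The +0.46 is a lower limit for a full course, because the two weeks are a minimum and any delay in starting MST adds to it. Under the consent list, a course that ends before 3 months gives an offset below −2, and any lag between discharge and the contact moves it upwards.

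**Step 5. What the arithmetic cannot give.** The distribution of MST durations is not stated, so no arm-level mean offset can be derived from these ranges.

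**The case against.** The strongest reply is that the operative schedule is common to both arms. The Overview and Measures sections time visits from randomisation for everyone, and step 1 shows that the roadmap does too. The consent list tells staff what to explain. It is not a visit schedule and does not call its contact the 6-month assessment. It may have been carried over from an earlier trial, since the recruitment procedure is said to rest on experience there. The written consent material is not available to check. The roadmap condition is a floor on a visit fixed at 6 months, so a family finishing MST at month 3 is still seen at month 6.

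Most of this stands, and it rules out several stronger readings that a reader might infer:

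- **That the arms are in fact compared at different times.** Three sections say otherwise.
- **That MST families who never complete have no anchor.** They are anchored to randomisation like everyone else.
- **That MST visits run from about 3.5 months.** That figure adds the roadmap's two weeks to the consent list's discharge trigger. No single statement produces it.
- **That an evenly accruing count or cost would differ by 25% between arms (1.5 ÷ 6).** This applies one family's extreme to the whole arm. On the same 3.5–6.5 range the midpoint is 5.0 months, equal to the MAU contact in the consent list.
- **That costs cover unequal periods.** The roadmap collects economic data at 3 months and three-monthly thereafter, counted from randomisation.

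The reply does not remove the contradiction. The same consent list separately gives six-month and yearly intervals for checking law-breaking, so its questionnaire timing is hard to read as loose shorthand for 6 months. The roadmap condition can be triggered in one arm only and fails against the protocol's own maximum treatment length.

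**Conclusion.** The point holds as an unresolved contradiction with a risk of bias, and it should be corrected. For an individual family the MST-minus-MAU offset is 0 under Measures, 0 to at least about +0.5 month under the roadmap, and about −2 to +1 months if the consent wording were followed. These ranges assume that MST starts at randomisation and lasts 3 to 6 months.

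The exposure is limited to interview and questionnaire secondary outcomes at the first visit and the trajectories that use them. A reader might extend it to the main result, but the documents do not support that: "The primary outcome will be out of home placements at 18 months", taken from formal records and analysed by Cox regression, so it does not depend on when the first interview takes place. The key forensic outcome, time to an offence leading to a recorded disposal, likewise does not depend on that visit.

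**What to change.** 1. Reconcile the consent list, the Measures section and the roadmap to one rule: first follow-up at 6 months from randomisation, with the same window in both arms, whether or not MST has finished. Bring the objectives, which count from recruitment, into line.
2. Remove the MST-completion condition from visit scheduling in the roadmap.
3. Correct the explanation given to families so that it describes the same follow-up timing for both arms.
4. Use actual time since randomisation, not nominal visit time, in the trajectory models. This can be specified in the SAP.
5. Where first visits have already taken place, tabulate time since randomisation at that visit by arm. This would show whether either arm-dependent rule was followed in practice.

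The cost is wording and scheduling. Sample size, primary analysis and treatment are unchanged. The one drawback is that some families will still be receiving MST at the 6-month visit, which is consistent with the planned intention-to-treat analysis.
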